1.1 Background

Multiple sclerosis (MS), one of the most common causes of neurological disability in young adults, is the prototypic acquired inflammatory demyelinating condition of the central nervous system (CNS), characterized by inflammation, demyelination and axonal/neuronal destruction, ultimately leading to severe disability in the majority of patients.

While traditional research has focused on the role of T cells for MS, pathogenic B cells are known to play an early role in the immune-mediated pathogenesis of MS ([Archelos et al 2000](#), [Frohman et al 2006](#), [McFarland 2008](#)). B cells, acting in concert with T cells have been found to be required for full disease expression ([Genain and Hauser 1996](#)), with essential functions in regulating immune response. B cells may contribute to disease pathogenesis by self-antigen presentation, serving as cellular adjuvants for cluster of differentiation (CD) 4+ T-cell activation ([Bouaziz et al 2007](#)) and by regulating T-cell function and inflammation via cytokine production ([Lund 2008](#)), in addition to producing autoantibodies. B-cells are present in chronic plaques, areas of demyelination, and in the cerebrospinal fluid of MS patients ([Lehmann-Horn et al 2013](#)). These observations have provided a new theoretical framework for the use of B cell based therapeutics in MS.

Selectively targeting B cells with anti-CD20 monoclonal antibodies has been proven highly effective at limiting disease activity in patients with relapsing forms of MS¹. Rituximab and ocrelizumab are anti-CD20-directed cytolytic antibodies that have been investigated in MS. Clinical evidence from randomized, placebo-controlled Phase 2 studies with the chimeric mouse/human anti-CD20 monoclonal antibody (mAb) rituximab ([Hauser et al 2008](#)) and the humanized anti-CD20 mAb ocrelizumab ([Kappos et al 2011](#)) showed B-cell depletion by these agents lead to marked reductions in MRI-measured inflammatory activity in RMS participants. Recently, the efficacy of ocrelizumab was confirmed in two Phase 3 trials in participants with RMS ([Hauser et al 2017](#)). These studies showed that ocrelizumab significantly reduced relapse rates, reduced MRI disease activity and delayed the time to disability worsening versus interferon beta 1a over 2 years. Ocrelizumab was well tolerated with no major safety findings reported in these clinical trials.

While ocrelizumab has received FDA approval in 2017 ([Ocrevus prescribing information; Hauser et al 2017](#)) for the treatment of adult patients with relapsing or primary progressive forms of multiple sclerosis, rituximab has not. Nonetheless, rituximab has been utilized in the real-world setting as off-label treatment for MS patients in the US. Both rituximab and ocrelizumab are delivered in a clinical setting by intravenous (iv) infusion. Rituximab is given off-label in a range of doses. A typical rituximab treatment for RMS may consist of 500-1,000 mg infusions on Day 1 and Day 15 followed by a 1,000 mg infusion every six months. Ocrelizumab is initiated with 300 mg infusions on Day 1 and Day 15, and maintained with a 600 mg infusion every six months. The real-world utilization of both rituximab and ocrelizumab in the US is common and ocrelizumab use has continued to increase since its 2017 approval for relapsing and primary progressive forms of MS. However, the real world safety, tolerability and continued access to these anti-CD20 (aCD20) therapies for MS patients in the clinical setting is not fully elucidated. Furthermore, clinical evidence demonstrating whether MS patients can be transitioned from IV aCD20 antibody therapy to ofatumumab is not yet available.

Ofatumumab is a fully human aCD20 mAb that induces B cell lysis via complement-dependent cytotoxicity (CDC) and antibody-dependent cell-mediated cytotoxicity (ADCC) (Teeling et al 2006). Ofatumumab recognizes an epitope localized close to the cell membrane on the 2 extracellular domains of the CD20 molecule, N-proximal of the epitope for the anti-CD20mAb rituximab. Preclinical differentiation between aCD20 mAb suggests a favorable profile of ofatumumab including higher CDC (Pacheco-Fernandez et al 2018), direct lymph node targeting (Torres et al 2019) and potential sparing of marginal zone B cells, which are relevant for host defense (Theil et al 2019). The clinical correlates of these preclinical findings remain to be explored in Ph3b/4 studies. Ofatumumab has been evaluated in two Phase 2 studies in participants with RMS, one of which proved the positive effect on inflammatory lesions when given subcutaneously (Sorensen et al 2014, Bar-Or et al 2018). In the head-to-head phase III clinical trials, ASCLEPIOS I and II (COMB157G2301 and COMB157G2302, respectively), monthly subcutaneous ofatumumab 20mg demonstrated superiority over once daily oral teriflunomide 14mg in participants with relapsing forms of multiple sclerosis. Both studies met the primary endpoints where ofatumumab showed a highly significant and clinically meaningful reduction in the number of confirmed relapses, evaluated as the annualized relapse rate (ARR). Specifically, RMS participants on ofatumumab had a reduction in annualized relapse rate (ARR) by 50.5% (0.11 vs. 0.22) and 58.5% (0.10 vs. 0.25) compared to teriflunomide (both studies $p < 0.001$) in ASCLEPIOS I and II studies respectively (Hauser et al 2019). Key secondary endpoints were also met, where ofatumumab showed a relative risk reduction of 34.4% in 3-month confirmed disability (CDW) ($p = 0.002$) and 32.5% in 6-month CDW ($p = 0.012$) versus teriflunomide in a pre-specified pooled analyses.

In the ASCLEPIOS studies, ofatumumab was subcutaneously administered via pre-filled syringe (PFS). In the APLIOS Phase II study (COMB157G2102), the autoinjector (AI) pen was compared with the pre-filled syringe (PFS) in a 12 week randomized open label multicenter study to demonstrate bioequivalence (Bar-Or et al 2020). The current study will utilize the ofatumumab AI pen to facilitate improved self- and home-administration and hence reduce the participant burden of treatment.

Notably, the ASCLEPIOS trials enrolled participants that were either treatment exposed or naive (~60% and 40%, respectively), but excluded participants with prior aCD20 mAb exposure (including rituximab and ocrelizumab) from study participation. Therefore, an evidence gap remains whether RMS participants discontinuing aCD20 mAb therapy might experience therapeutic benefit from treatment transition to ofatumumab. This study aims to explore whether ofatumumab is effective, safe, tolerable, and has better Participant satisfaction in these RMS participants.

1.2 Purpose

The purpose of the study is to complement the ofatumumab Phase 3 program by evaluating continued clinical efficacy, participant retention and satisfaction, as well as safety and tolerability for ofatumumab 20mg subcutaneous administered via the AI pen once monthly in participants with relapsing forms of MS who transition from aCD20 mAb therapy.

[figure not shown]
The primary outcome will be to explore maintenance of efficacy evaluated by MRI lesions (gadolinium enhancing T1 lesions) at 12 months after initiating ofatumumab therapy vs baseline in RMS participants transitioning to ofatumumab from aCD20 therapy (for reasons other than

suboptimal response or certain treatment-emergent adverse events). This phase 3b trial will also characterize participant retention, immune biomarkers, treatment satisfaction, and safety and tolerability at 6 and 12 months in participants transitioning to ofatumumab from an aCD20 mAb.

2 Objectives, endpoints and estimands

Table 2-1 Objectives and related endpoints

Objective(s)	Endpoint(s)
Primary objective(s)	Endpoint(s) for primary objective(s)

Explore maintenance of efficacy of ofatumumab in participants with RMS transitioning from aCD20 therapy	
No change or a reduction from baseline in the number of gadolinium enhancing lesions observed by MRI at 12 months of ofatumumab treatment (yes, no)
Secondary objective(s)	Endpoint(s) for secondary objective(s)

Characterize participants retention, immune biomarkers, treatment satisfaction, and safety and tolerability at 6 and 12 months after transitioning to ofatumumab	
Retention on ofatumumab treatment from baseline to Month 6, and to Month 12 (yes, no)Change from baseline in lymphocytes, including total CD19+ B cell counts and CD3+CD20+ T cell counts, obtained by fluorescence activated cell sorting (FACS) at Months 6 and 12C-SSRS at Months 6 and 12Treatment Satisfaction Questionnaire for Medication (TSQM-9) scores (including domains) at baseline vs Month 6 and vs Month 12Treatment-emergent adverse events

2.1 Primary estimands

The primary clinical question of interest is whether ofatumumab can maintain efficacy in relapsing MS participants as measured by the presence of gadolinium enhancing lesions on MRI at 12 months after switching from an intravenous aCD20 mAb for reasons other than efficacy or safety.

[figure not shown]
The justification for the primary estimand is that it will capture whether or not participants can be maintained on subcutaneous ofatumumab after documented stable, effective treatment with an intravenous aCD20 mAb, a scenario that is a real life question in the MS community where continued access to an infusion suite may not be possible or desired.

The primary estimand is described by the following attributes:

- **Population:** relapsing MS Participants currently treated with an infused aCD20 mAb, specifically ocrelizumab or rituximab, that have received at least 2 courses of therapy, that are switching due to reasons other than safety or efficacy. Further details about the population are provided in [Section 5](#).
- **Variable:** no change or a reduction in gadolinium enhancing lesions on MRI at Month 12 (yes/no).
- **Treatment of interest:** following a loading dose regimen consisting of once daily doses on days 1, 7 and 14, ofatumumab is given once monthly starting at Month 1. All doses of ofatumumab will be given subcutaneously via an autoinjector at a dose of 20mg. Further details about the investigational treatment are provided in [Section 6](#).
- **Intercurrent event:** Death or treatment/study discontinuation.
- **Summary measure:** Proportion of subjects achieving no change or a reduction in gadolinium enhancing lesions on MRI at Month 12.

2.2 Secondary estimands

Not applicable

3 Study design

This is a single-arm, multi-center, prospective, study in approximately 100 participants with relapsing multiple sclerosis who have been previously treated with aCD20 mAb therapy and have received at least 2 consecutive courses of intravenously administered ocrelizumab or rituximab every 6 months and the last dose is within 4 to 9 months before Baseline/Day 1. In this study, participants may enroll only if discontinuing aCD20 therapy for reasons other than lack of efficacy or due to certain treatment-emergent adverse events. Reasons for switching may include but are not limited to physician/participant preference, access to commercial drug (e.g. insurance coverage issues) or for other logistical reasons (such as geographical relocation, travel, etc.) A total of approximately 100 eligible participants will receive open label ofatumumab 20 mg subcutaneous once monthly for 12 months following initial loading regimen of 20 mg subcutaneous doses on Days 1, 7 and 14.

Assessments will be done per the assessment schedules ([Table 8-1](#) and [Table 8-2](#)).

For participants who discontinue study treatment prematurely for any reason before the end of the treatment phase, an End of Study visit must be performed within 7 days of study discontinuation.

Upon completing the study, participants may continue ofatumumab therapy on commercial drug.

Safety follow-up:

[figure not shown]
- The Safety follow-up (FU) period will be applicable for the following participants:
 - participants who complete the Treatment period on the study drug and do not continue on any MS DMT.
 - participants who prematurely discontinue study drug and do not continue on any MS DMT.
- All Safety FU visits must be scheduled relative to the End of Study (EOS) Visit.

Participants that do not continue into the ofatumumab commercial patient services hub within one month of the EOS Visit or that do not switch to another therapy, must continue into the safety FU phase, consisting of every 3 month visits including B cell monitoring until they are able to start on commercial ofatumumab or until they switch to another therapy or until their B cells are repleted defined as a B cell concentration greater than the individual participant's baseline value prior to starting the IV anti-CD20 mAb or greater than the lower limit of normal. All participants will have a safety follow-up phone call at 30 days post study.

A shortened follow-up time is acceptable if participants select different treatment during this period or show earlier repletion. If participants are not fully repleted by the 6 month post-trial safety follow-up visit, further follow up visits at a 3 monthly frequency are recommended until full repletion has occurred. ([Table 8-2](#))

For participants completing the trial, the total duration of the trial will be a minimum of 14 months. This accounts for the 28 day screening period, the 12 month treatment period, and a 30 day telephone safety follow-up. Safety follow-up may be longer if the participant has not switched to another therapy post-trial and B cell repletion has not occurred.

Figure 3-1 Study design

3.1 Remote procedures

At the investigator's direction and based on benefit-risk considerations of the participant's clinical condition, qualifying participants may be offered the option to have certain clinical trial procedures according to Table 8-1 Assessment schedule performed at the participants home. This is optional for all participants.

Procedures will be performed remotely under the oversight of the Investigator and study staff, who retains accountability for the oversight and all efficacy and safety decisions with delegation of tasks to the home nurse (OHP) provided by a third-party vendor sourced by Novartis. If the site wishes to use the home nurse (OHP) provided by Novartis this must be agreed and approved with Novartis before use.

In addition to procedures performed by the home nurse (OHP), the Investigator and study staff will perform certain procedures remotely using the sites own tele-visit platform. Novartis has the right to decide at any time what can and cannot be performed remotely.

On Day 7, 14 and Month 2, 3, 4, 5, 7, 8, 9, 10, and 11, the participant, caregiver and/or home nurse will administer 20mg of ofatumumab subcutaneous using an autoinjector pen. For females of childbearing potential, the participants, caregiver and/or home nurse will obtain a urine pregnancy test prior to administering study medication. Investigator and/or study staff will contact the participant remotely to access any adverse events, concomitant medications and answer any questions the participant may have. If needed due to the pandemic, epidemic or natural disaster participants can opt into having Month 1 and Month 6 completed remotely by the home nurse (with the investigator or sub investigator via tele visit). The home nurse will obtain a blood draw, vital signs, weight, urinalysis, [REDACTED], physical exam [REDACTED]. All participants will need to go on site for the month 6 MRI scan.

4 Rationale

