Visit Window Days (d)			±1d	±1d	±3d	±3d	±3d	±3d	±3d	±3d	±3d	±3d	±3d	±3d	±3d	±3d	±7d	
Self-injection Training (Participant and/or caregiver)		S																
Study drug self-injection (at Home) ⁸			X	X		X	X	X	X		X	X	X	X	X			
Administration of study treatment at site ²²		X			X					X						X		
Drug Accountability		S			S					S						S		
Dispensation of study drug 2,4, 7,12,13,14		S 2,4, 7 12,13			S ¹⁴					S ¹⁴						S ¹⁴		S ¹⁴
Dosage Administration Record		X			X					X						X		
Concomitant Medications ⁸	X	X ¹²	X	X	X	X	X	X	X	X	X	X	X	X	X	X	X	X
Adverse Events/ Serious Adverse Events ⁸	X	X ¹²	X	X	X	X	X	X	X	X	X	X	X	X	X	X	X	X
C-SSRS	X ¹²				X					X						X		X

Period ¹	Screening / BSL		Treatment Period													End of Treatment /Study	Follow-up	Unplanned
Visit Name	Screening	BSL V1	V2	V3	V4	V5	V6	V7	V8	V9	V10	V11	V12	V13	V14	EOT/EOS V15 ⁵	Safety	Unscheduled Visit
Visit Day (D)/Month (M)	-28 Days	D1	D7	D14	M1	M2	M3	M4	M5	M6	M7	M8	M9	M10	M11	M12	30-Day Tel.	UPV
Visit Window Days (d)			±1d	±1d	±3d	±3d	±3d	±3d	±3d	±3d	±3d	±3d	±3d	±3d	±3d	±3d	±7d	
TSQM-9 ¹³		X ¹²			X					X						X		X
Thank You Letter		S														S		
Health Status Telephone Call ⁸			S ⁸	S ⁸		S ⁸	S ⁸	S ⁸	S ⁸		S ⁸	S ⁸	S ⁸	S ⁸	S ⁸		S ⁸	

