
9. Restrictions may apply to MRI concerning steroid use, please refer to Section 8.3.4. Scans of the brain and cervical spine are needed.
 
10. Screening MRI should be completed once all other screening eligibility assessments have been completed and confirmed to meet eligibility criteria.
 
11. MRI scan at the EOS/EOT visit is required.
 
12. All assessments to be completed prior to baseline visit/first study drug administration.
 
13. Vital signs should be obtained 30-60(+/- 10min) minutes before the subcutaneous injection (study drug). If premedication is required, the vital signs should be taken prior to premedication administration. At the baseline visit only, systolic and diastolic blood pressure should be measured 3 times.
 
14. If the scheduled visit coincides with the day that study drug administration is scheduled, the participant should be instructed not to administer the injection before coming to the site so that the safety assessments can be completed prior to study drug administration unless the scheduled visit is outside of the 3 day window for drug administration.
 
[REDACTED]
 
16. Labs must be drawn to allow adequate time for results to be obtained before first study drug administration to ensure participant's eligibility.
 
17. Participant's contraception status must be reviewed and documented to ensure method of contraception continues to be appropriate per protocol requirement for highly effective contraception. Pregnancy test is conducted on female participants only. Urine pregnancy tests will be conducted at all scheduled visits as indicated in Table 8-1. The participant must contact the Investigator immediately in the case of a positive test for confirmatory testing at the Investigator's discretion.
 
[REDACTED]
 
[REDACTED]
 
21. Urine dipstick: If positive send full urinalysis to central laboratory.
 
22. Site staff must observe the participant /caregiver administer study drug at Mo. 1 and Mo. 6 after all assessments have been completed with the exception of the MRI at Mo. 6.
 
24. Additional unplanned ECGs may be performed at the Investigator's discretion if clinically indicated.
 
25. Historical IgM and IgG results if available from pre-baseline of IV anti-CD20 treatment (one result pre-infusion) and then any testing done following IV anti-CD20 initiation. This should be recorded once for all participants enrolled or completed and may be collected at any visit.
																		

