8.4.5 Laboratory evaluations

[figure not shown]
If available, historical IgM and IgG values that have been collected prior to the screening visit, including one pre-anti-CD20 infusion value, should be recorded including the collection date. This should be recorded for all new, existing, and completed participants, and may be entered at any time-point during the study.

A central laboratory will be used for analysis of all specimens collected. Details on the collections, shipment of samples and reporting of results by the central laboratory are provided to Investigators in the laboratory manual.

[figure not shown]
Abnormal laboratory parameters, inconsistent with clinical presentation of MS, or which cause suspicion of an underlying medical condition should be repeated for confirmation. All abnormal lab results must be evaluated for criteria defining an adverse event and reported as such if the criteria are met. For those lab adverse events, repeated evaluations are mandatory until normalization of the result(s) or until the result is no longer considered clinically significant.

Table 8-5 Laboratory Assessments

Test Category	Test Name
Hematology	Blood samples will be collected according to the schedule in Table 8-1 and Table 8-2 . Hematocrit, Hemoglobin, Platelets, Red blood cell (RBC) count, Total WBC count and WBC differential counts (Basophils, Eosinophils, Lymphocytes, Monocytes, Neutrophils).
Chemistry	Blood samples will be collected according to the schedule in Table 8-1 and Table 8-2 .

	Electrolytes (Sodium, potassium, chlorine, bicarbonate, calcium, magnesium, phosphorus), random glucose, total protein, urea nitrogen, albumin, alkaline phosphatase, ALT, AST, γ -GT, total bilirubin, conjugated bilirubin, creatinine, amylase, total cholesterol, triglycerides, high density lipoprotein and low density lipoprotein, C-Reactive protein.
B-cell/T-cell sampling	CD19 ⁺ B-cell counts and CD3 ⁺ CD20 ⁺ T-cell counts. Samples will be collected according to the schedule in Table 8-1 and Table 8-2 .
Total IgG and IgM levels	Samples will be collected according to the schedule in Table 8-1 and Table 8-2 .

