8.4.6 Pregnancy and assessments of fertility

Serum pregnancy tests will be conducted for all women of childbearing potential at each clinic visit including the EOS visit. Urine pregnancy tests will be conducted for all women who are of child bearing potential at all other planned clinic visits as indicated in [Table 8-1](#) and [Table 8-2](#) prior to study drug administration. In addition, the participants will be provided with urinary pregnancy test kits for monthly home pregnancy testing required between the scheduled clinic visits prior to study drug administration. The participants will document the date and result of each home pregnancy test. In case of a positive test result, the participant must contact the Investigator immediately for confirmatory testing at the Investigator's discretion.

[figure not shown]
In addition, the Investigator will review the contraception status with the participant at each visit to ascertain that the participant continues to comply with protocol requirements for highly effective contraception as applicable.

All pre-menopausal women who are not surgically sterile will have pregnancy testing. Additional pregnancy testing might be performed if required by local requirements.

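### Table 8-1 marks no pregnancy test at the Day 7 and Day 14 home doses, where section 3.1 requires one, and the protocol does not say whether the serum result at Months 1, 6 and 12 must be known before the injection

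*Protocol*

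**What the plan says.** Protocol section 3.1 names the home-dosing days: "On Day 7, 14 and Month 2, 3, 4, 5, 7, 8, 9, 10, and 11". The next sentence says that, for females of childbearing potential, the person giving the dose "will obtain a urine pregnancy test prior to administering study medication".

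Table 8-1 has two dosing rows and two pregnancy-test rows. Home injection is marked at Days 7 and 14, Months 2 to 5 and Months 7 to 11. The row "Administration of study treatment at site" is marked at Day 1 and Months 1, 6 and 12. The urine test is marked at Baseline, Months 2 to 5 and Months 7 to 11. The serum test is marked at Screening and Months 1, 6 and 12. Both tests are also marked for unscheduled visits.

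Four footnotes to Table 8-1 bear on this:
- Footnote 17: "Urine pregnancy tests will be conducted at all scheduled visits as indicated in Table 8-1".
- Footnote 22: "Site staff must observe the participant /caregiver administer study drug at Mo. 1 and Mo. 6 after all assessments have been completed", with the Month 6 MRI excepted.
- Footnote 14 tells participants to hold the injection on a visit day so that safety assessments come first. Section 8.4 counts pregnancy testing among the safety assessments.
- Footnote 16 asks that blood be drawn early enough for results to be back before the first dose. In the serum pregnancy row it is attached to Screening only.

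Section 8.4.6 says: "Serum pregnancy tests will be conducted for all women of childbearing potential at each clinic visit including the EOS visit". It places urine tests at the other planned clinic visits shown in Tables 8-1 and 8-2, before study drug, and supplies kits for monthly home tests between clinic visits. Section 8.4.5 says: "A central laboratory will be used for analysis of all specimens collected". No turnaround time is given.

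**The concern.** Pregnancy is an exclusion criterion (section 5.2) and a required reason to stop study treatment (section 9.1.1), so testing before a dose is a safety check. For Days 7 and 14 the text requires that check and the schedule does not show it. Sites usually work from the schedule, and footnote 17 sends them there.

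For Months 1, 6 and 12 the question is different. A test is scheduled, but the protocol does not say whether the blood sample has only to be taken before the injection or whether its result must also be known.

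The consequence is that sites may apply the check differently. Both pregnancy rows are marked for source documentation only, so such differences would be visible at source review but not in the clinical database. The primary endpoint and its precision are not affected.

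**Working it through.** No figure in the plan needs reproducing. The check is a count of marks in Table 8-1, crossing the two dosing rows with the two pregnancy-test rows.

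| Dosing days | Doses | Where given | Test marked in Table 8-1 |
|---|---|---|---|
| Day 1 | 1 | site | urine |
| Days 7, 14 | 2 | home | none |
| Month 1 | 1 | site | serum |
| Months 2–5 | 4 | home | urine |
| Month 6 | 1 | site | serum |
| Months 7–11 | 5 | home | urine |
| Month 12 | 1 | site | serum |

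**Totals**
- Doses: 4 at site + 11 at home = 15.
- Urine test marked: 1 + 4 + 5 = 10.
- Serum test only: Months 1, 6 and 12 = 3.
- No test marked: Days 7 and 14 = 2.
- Check: 10 + 3 + 2 = 15.

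**Days 7 and 14.** Section 3.1 and Table 8-1 agree on the 11 home-dosing days. Section 3.1 applies the urine test to that list, but the table marks it at 4 + 5 = 9 of them. The two left over are Days 7 and 14, which is 2/15 = 13% of all doses. The kits do not settle the matter. Sections 6.7.2 and 8.4.6 describe them as monthly, so tests on Days 7 and 14 are not clearly supplied.

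**Months 1, 6 and 12.** These are 3/15 = 20% of doses.
- The section 3.1 sentence does not reach them, because its list leaves them out.
- In section 8.4.6 the condition of testing before study drug is attached to the urine tests, not to the serum tests.
- Footnotes 14 and 22 put assessments ahead of the dose, but do not say whether completing a blood test means drawing it or having the result.
- Footnote 16 shows that the protocol allows lead time for results where it wants them first. It is not attached to these three visits.

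**Section 8.4.6 against the table.** Baseline is a clinic visit, so section 8.4.6 calls for serum there. Table 8-1 marks urine only.

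**The case against.** The strongest reply is that a blank cell forbids nothing: a site that reads section 3.1 will test on Days 7 and 14 and breach no rule. Those doses also fall only 6 and 13 days after the Day 1 urine test, highly effective contraception is an entry condition, and contraception status is reviewed at each visit. All of this is fair, and it limits the likely harm. It does not remove the mismatch, because footnote 17 points to the table and the kits are monthly.

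A second reply concerns section 8.4.6. Its reference to other planned clinic visits can be read as meaning the follow-up visits in Table 8-2, which are urine only. That reading removes most of the apparent conflict within the section. The mismatch at Baseline remains.

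A reader might add the two groups together and infer that at 5 of 15 doses (33%) no pregnancy result is available before injection. The documents do not support this:
- At Days 7 and 14 a result would exist wherever section 3.1 is followed.
- At Months 1, 6 and 12 a serum test is scheduled. That its result arrives after the dose is only an inference from central analysis with an unstated turnaround.
- No text expressly requires a serum result before those three doses, so nothing there is contradicted.

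Nor does it follow that anyone who conceives before Month 1, 6 or 12 will be dosed undetected. Urine tests are marked at Day 1, Month 5 and Month 11, so any gap concerns conceptions too recent for the preceding test.

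**Conclusion.** The point holds, in two parts of different strength. At 2 of 15 scheduled doses (Days 7 and 14) the text requires a urine test before home dosing and the schedule marks no pregnancy test. That is a direct inconsistency and rests on no assumption beyond reading the table columns as laid out. At 3 further doses (Months 1, 6 and 12) the protocol is silent rather than contradictory: it schedules a serum test and does not say whether the result must precede the injection. Whether a result would in practice be late depends on laboratory turnaround, which the protocol does not give. The Baseline mismatch between section 8.4.6 and Table 8-1 is a smaller inconsistency of the same kind.

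The matter should be corrected because it concerns a safety check and is cheap to settle. It does not show that participants are dosed without a pregnancy result.

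**What to change.** Reconcile section 3.1, section 8.4.6, Table 8-1 and footnotes 14, 17 and 22 so that each of the 15 dosing days carries one consistent pre-dose pregnancy-test requirement. The amended text should:
- say the same thing about Days 7 and 14 in section 3.1 and in Table 8-1;
- state whether a result must be available before dosing at Months 1, 6 and 12, or only the sample taken;
- make section 8.4.6 and Table 8-1 agree on the Baseline test;
- align the kit supply in sections 6.7.2 and 8.4.6 with the rule chosen. The present kits are for monthly testing between clinic visits and do not clearly cover the five doses without a marked urine test.

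The sponsor decides the rule; this review proposes none. The cost is a schedule and wording amendment. Depending on the choice, it also needs from none to five additional urine kits per woman of childbearing potential (at most 2 for Days 7 and 14, plus 3 for Months 1, 6 and 12).
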